## 1 BACKGROUND AND HYPOTHESIS

Hepatitis C viral (HCV) infection is a global health problem. 170 million individuals are chronically infected worldwide and at risk of developing liver cirrhosis, hepatocellular carcinoma, or both. Cirrhosis develops after prolonged hepatitis C virus infection. Complications of cirrhosis include hepatic decompensation (ascites; encephalopathy; variceal hemorrhage; hepato-renal syndrome or hepatic synthetic dysfunction) and hepatocellular carcinoma, which ensues at a rate of about 3% per year. Without liver transplantation, decompensated cirrhosis leads to death in 50% to 72% of patients after 5 years. As a result of the high prevalence of hepatitis C virus (HCV) infection and resultant complications, HCV is the leading indication for liver transplantation in the United States and the world as a whole.

Treatment of hepatitis C virus-infected patients could reduce the risk of cirrhosis, decompensation, cancer, and liver-related deaths. Among patients treated with pegylated interferon and ribavirin therapy, achieving a sustained virologic response (SVR) was associated with significant reduction in all-cause death compared to subjects who did not achieve sustained virologic response (5-year mortality rate in HCV genotype 1-infected patients: 6.7% versus 14.4%, respectively).

In addition, the 5-year occurrence of the composite clinical events of death, liver failure, and hepatocellular carcinoma were significantly lower in hepatitis C virus-infected patients with advanced fibrosis or cirrhosis who achieved sustained virologic response versus those without sustained virologic response (9.2% versus 28.2%, respectively). Patients with sustained virologic response following treatment with pegylated interferon with or without ribavirin have also shown improvement in liver histology and a reduction in liver-related death in several studies.

Moreover, patients with compensated cirrhosis who achieve sustained virologic response essentially eliminate their subsequent risk of decompensation, may achieve histologic regression, and decrease their risk of hepatocellular carcinoma by two-thirds. In patients with advanced fibrosis and cirrhosis, viral suppression by more than 4 logs10 with pegylated interferon and ribavirin was associated with marked reduction in death/liver transplantation, and in liver-related morbidity and death.

Combinations of direct-acting antiviral (DAA) agents targeting different steps of viral replication have the potential to significantly improve hepatitis C virus treatment, compared to the current interferon-containing regimens for HCV genotype 1 infection. Combination DAA allows for increased/sustained virologic response rates, elimination of interferon as a component of therapy, increased safety, and tolerability of treatment, shortened duration of therapy and simplifying the treatment algorithm.

Wider application of direct-acting antiviral agent therapy and better responses with combination direct-acting antiviral agent regimen(s) could significantly reduce the public health burden of this disease.

AbbVie's interferon-free regimen for the treatment of chronic hepatitis C virus genotype 1 infection includes three direct-acting antiviral agents targeting different steps in hepatitis C virus

replication: ABT-450 is a nonstructural protein 3/nonstructural protein 4A (NS3/NS4A) protease inhibitor co-administered with a pharmacokinetic (PK) enhancer, ritonavir (ABT-450/r); an NS5A inhibitor ABT-267 (ombitasvir) and ABT-333 (dasabuvir) an NS5B non-nucleoside polymerase inhibitor.

The three direct-acting antiviral (3-DAA) agents regimen has been studied with and without ribavirin in over 2,300 patients in Phase 3 trials across a variety of patient populations including those with compensated cirrhosis. Based on Phase 3 data, the regimen with or without ribavirin appears to be safe, well tolerated, and efficacious in treatment-naïve and treatment-experienced hepatitis C virus genotype 1-infected subjects including those with compensated cirrhosis. The overall efficacy results (intent-to-treat) from the Phase 3 studies are listed in Table 1.

**Table 1 - Combined SVR 12 Rates (Intent-to-treat, missing = failure) from Phase 3 Studies by Subpopulation of Subtype, Prior Treatment History, and Presence or Absence of Cirrhosis**

Subpopulation	3-DAA 12 Weeks SVR12	3-DAA + RBV 12 Weeks SVR12	3-DAA + RBV 24 Weeks SVR12	
Genotype 1b non-cirrhotics				
Naïve	99.0	98.9	--	
Null	100	94.4	--	
Partial	100	98.1	--	
Relapser	100	98.5	--	
Genotype 1a non-cirrhotics				
Naïve	90.2	95.7	--	
Null	--	95.4	--	
Partial	--	100	--	
Relapser	--	94.0	--	
Genotype 1b cirrhotics				
Naïve	--	100	100	
Null	--	100	100	
Partial	--	85.7*	100	
Relapser	--	100	100	
Genotype 1a cirrhotics				
Naïve	--	92.4		
Null	--	80.0	92.9	92.9
Partial	--	100	100	
Relapser	--	93.3	100	

DDA = Direct-Acting Antiviral; \* Based on N = 7; 6/7 achieved SVR

The data outlined in Table 1 (above) and Table 2 (below) are based on the following studies:

### **1.1 Phase 3 Placebo-Controlled Studies: SAPPHIRE-I and SAPPHIRE-II**

Study SAPPHIRE-I and SAPPHIRE-II are randomized, placebo-controlled studies that assessed the safety and efficacy of 12 weeks of therapy with three direct-acting antiviral (3-DAA) agents and ribavirin in hepatitis C virus (HCV) genotype 1-infected treatment-naïve subjects (Study SAPPHIRE-I) and prior pegylated-interferon/ribavirin non-responders (Study SAPPHIRE-II) without cirrhosis. Subjects received 3-DAA agents and ribavirin (RBV) for 12 weeks of treatment. Subjects randomized to the placebo arm received placebo for 12 weeks, after which they received open-label 3-DAA agents and RBV for 12 weeks. In Study SAPPHIRE-I 631 subjects were randomized and received at least one dose of study drug, of which 67.7% had HCV genotype 1a and 32.3% had HCV genotype 1b. The SVR12 rate for treatment-naïve subjects receiving 3-DAA agents and ribavirin for 12 weeks was 96.2%. Virologic failure was noted in 7/322 (2.2%) genotype 1a subjects (on treatment virologic failure: n = 1; relapse: n = 6) and 1/151 (0.7%) genotype 1b subjects (relapse).

In Study SAPPHIRE-II, a total of 394 subjects were randomized and received at least one dose of study drug, of which 58.4% had hepatitis C virus (HCV) genotype 1a, 41.4% had HCV genotype 1b, 49.0% were prior pegylated-interferon/ribavirin null responders, 21.9% were prior pegylated-interferon/ribavirin partial responders, and 29.2% were prior pegylated-interferon/ribavirin relapsers. The SVR12 rate for treatment-experienced subjects receiving three direct-acting antiviral (3-DAA) agents and ribavirin for 12 weeks was 96.3%. Virologic failure (all relapse) was noted in 5/173 (2.9%) genotype 1a subjects and 2/123 (1.6%) genotype 1b subjects.

### **1.2 Phase 3 Regimen-Controlled Studies: (3DAA ± RBV): Studies PEARL-II, PEARL-III, PEARL-IV, and M14-002**

Studies PEARL-II, PEARL-III, and PEARL-IV are randomized, regimen-controlled trials that assessed the safety and efficacy of 12 weeks of treatment with three direct-acting antiviral agents with or without ribavirin. Studies PEARL-III and PEARL-IV are ribavirin placebo-controlled studies, while Study PEARL-II is an open-label study. The patient population was different in each of the three studies. Study PEARL-II enrolled genotype 1b-infected subjects with prior non-response to pegylated-interferon/ribavirin, Study PEARL-III enrolled genotype 1b-infected subjects who were treatment-naïve, and Study PEARL-IV enrolled genotype 1a-infected subjects who were treatment-naïve. All three studies excluded subjects with cirrhosis. In Study PEARL-II, a total of 186 subjects were randomized and received at least one dose of study drug, of which 34.9% were prior pegylated-interferon/ribavirin (pegIFN/RBV) null responders, 28.5% were prior pegIFN/RBV partial responders, and 36.6% were pegIFN/RBV relapsers. The SVR12 rates were 96.6% in the three direct-acting agents with ribavirin arm and 100% in the three direct-acting antiviral agents without ribavirin arm. The difference in SVR12 rates between the two regimens met the protocol-specified criteria for noninferiority. Hence, the three direct-acting antivirals (3-DAA) regimen without ribavirin demonstrated noninferiority compared to the (3-DAA) agents and ribavirin. No subject in either arm experienced on treatment virologic failure or post-treatment relapse.

In the PEARL-III study, 419 subjects were randomized and received at least one dose of study drug. The SVR12 rates for treatment-naïve subjects with HCV genotype 1b-infection, who received either 3-DAA with, or without ribavirin for 12 weeks were 99.5% and 99.0%, respectively. The difference in SVR12 rates between the two regimens in this study also met the protocol-specified criteria for noninferiority. One of the 419 treated subjects in the three direct-acting antiviral agents and ribavirin arm experienced on-treatment virologic failure.

In Study M14-002, 305 subjects were randomized and received at least one dose of study drug. The SVR12 rates for treatment-naïve subjects with HCV genotype 1a-infection who received three direct-acting antiviral agents either with or without ribavirin for 12 weeks in Study PEARL-IV were 97.0% and 90.2%, respectively. The SVR12 rate in the 3-DAA arm did not achieve noninferiority to the 3-DAA and ribavirin arm. Virologic failure was noted in 2/100 (2.0%) subjects (on treatment virologic failure: n = 1; relapse: n = 1) in the ribavirin-containing regimen and 16/205 (7.8%) subjects (on treatment virologic failure: n = 6; relapse: n = 10) in the ribavirin-free regimen. The difference between arms demonstrates that ribavirin contributes to the efficacy in genotype 1a-infected patients and suggests that three direct-acting antiviral agents and ribavirin is the optimal regimen for these patients.

### **1.3 Phase 3 Study in Cirrhotics: Study TURQUOISE-II**

Study TURQUOISE-II is a randomized, multicenter, open-label trial in treatment-naïve subjects or subjects previously treated with pegylated-interferon/ribavirin with chronic hepatitis C virus genotype 1-infection with compensated cirrhosis (Child-Pugh A, score  $\leq 6$ ). The three direct-acting antiviral agents and ribavirin were administered for either 12 or 24 weeks of treatment.

A total of 380 subjects were randomized and received at least one dose of study drug, of which 68.7% had hepatitis C virus genotype 1a, 31.3% had hepatitis C virus genotype 1b, 42.1% were treatment-naïve, 36.1% were prior pegylated-interferon/ribavirin (pegIFN/RBV) null responders, 8.2% were prior pegIFN/RBV partial responders, and 13.7% were prior pegIFN/RBV relapsers.

The SVR12 rates for subjects with compensated cirrhosis treated with three direct-acting antiviral agents and ribavirin for 12 or 24 weeks were 91.8% and 95.9%, respectively. Virologic failure was noted in 13/208 (6.3%) subjects (on treatment virologic failure: n = 1; relapse: n = 12) receiving the 12 week regimen and 4/172 (2.3%) subjects (on treatment virologic failure: n = 3; relapse: n = 1) receiving the 24 week regimen.

Analyses of subgroups suggest that the overall difference in SVR12 rates was driven largely by a lower SVR12 rate among genotype 1a prior null responders who received 12 weeks of treatment, while other subgroups had comparable response rates when treated for 12 or 24 weeks.

## 1.4 Integrated Safety Results

A summary of treatment-emergent adverse events from the combined analyses of data from the Phase 3 studies is presented in Table 2. A majority of subjects experienced at least one event, but most subjects experienced events that were mild in severity. Rates of severe adverse events and adverse events leading to discontinuation were low across studies but numerically higher in the study of subjects with cirrhosis.

**Table 2: Overview of Treatment-Emergent Adverse Events (AE)**

	Placebo-Controlled		Regimen-Controlled		Cirrhotics	
	12-Week 3-DAA + RBV	12-Week PBO	12-Week 3-DAA + RBV	12-Week 3- DAA	12-Week 3-DAA + RBV	24-Week 3-DAA + RBV
Events, %	N = 770	N = 255	N = 401	N = 509	N = 208	N = 172
Subjects ≥ 1 AE	89.0	76.9	82.8	75.0	91.8	90.7
Severe AE	3.5	0.4	1.0	1.2	6.7	7.6
Grade 3 or 4 AE	3.9	0.8	3.0	2.0	7.7	8.1
Serious AE	2.1	0.4	2.2	1.4	6.3	4.7
AE leading to discontinuation	0.8	0.4	0.5	0.4	1.9	2.3
Deaths	0.1 a	0	0	0	0	0

DDA = Direct-Acting Antiviral; PBO: Placebo; aLung Cancer

The most common adverse events regardless of causality are listed in Table 3. Adverse events that occurred at ≥ 5% incidence in the 3-DAA and RBV regimen versus the placebo were considered to be adverse drug reactions related to the study treatment. These include fatigue, nausea, pruritus, insomnia, asthenia, and anemia. The frequency of these events was generally lower in the arm treated without ribavirin. In general, rates of adverse events were similar in patients with cirrhosis versus those without.

**Table 3: Treatment-Emergent Adverse Events with ≥ 10% Frequency in at Least One Arm of the Analysis and Rates of Key Post-Baseline Lab Abnormalities**

	Placebo-Controlled		Regimen-Controlled		Cirrhotics	
	12-Week 3-DAA + RBV	12-Week PBO	12-Week 3-DAA + RBV	12-Week 3- DAA	12-Week 3-DAA + RBV	24-Week 3-DAA + RBV
Treatment-emergent Adverse Events, %	N = 770	N = 255	N = 401	N = 509	N = 208	N = 172
Headache	34.3	29.8	24.4	25.1	27.9	30.8
Fatigue	34.2	26.3	29.9	26.5	32.7	46.5

	Placebo-Controlled		Regimen-Controlled		Cirrhotics	
	12-Week 3-DAA + RBV	12-Week PBO	12-Week 3-DAA + RBV	12-Week 3- DAA	12-Week 3-DAA + RBV	24-Week 3-DAA + RBV
Nausea	22.3	14.9	15.7	8.4	17.8	20.3
Pruritus	15.7	4.3	12.0	6.1	18.3	19.2
Insomnia	14.0	7.5	12.2	5.1	15.4	18.0
Diarrhea	13.5	9.0	8.7	11.4	14.4	16.9
Asthenia	13.5	6.7	9.0	3.9	13.9	12.8
Rash	10.0	5.9	6.2	3.7	11.1	14.5
Cough	8.7	5.1	6.7	4.7	11.5	11.0
Irritability	5.3	4.7	3.2	3.1	7.2	12.2
Anemia	5.3	0	7.5	0.2	7.7	10.5
Dyspnea	9.7	5.5	4.7	2.2	5.8	12.2
Laboratory Events, %	N = 765	N = 254	N = 401	N = 509	N = 208	N = 172
Hemoglobin						
< 10 g/dL (Gr 2)	5.5	0	6.2	0	7.2	11.0
< 8.0 g/dL (Gr 3)	0.1	0	0.5	0	1.4	0.6
ALT						
> 5 × ULN (Gr 3)	1.2	3.9	0.7	0.2	2.9	0
Bilirubin						
> 3 × ULN (Gr 3)	2.6	0	5.7	0.4	13.5	5.2

DDA = Direct-Acting Antiviral; PBO: placebo; Percentages of laboratory events based on the number of subjects with at least one post-baseline value

Transient elevations in total (predominantly indirect) bilirubin may occur due to ABT-450 inhibition of the bilirubin transporters OATP1B1 and OATP1B3, and ribavirin-induced hemolysis. The elevations generally peaked by weeks 1 - 2, declined through the end of treatment, and returned to within the normal range by four weeks post-treatment. Rates of hyperbilirubinemia were lower in subjects treated with three direct-acting antiviral (3-DAA) agents without ribavirin compared to 3-DAA with ribavirin. The rates and degree of hyperbilirubinemia were higher in patients with cirrhosis, but the temporal pattern of elevation followed by resolution was similar and few were symptomatic (jaundice). Rates of ≥ Grade 2 hemoglobin reductions were 6% among subjects without cirrhosis who received the 3-DAA and ribavirin regimen for 12 weeks, and 7% and 11% among subjects with cirrhosis who received the 3-DAA and ribavirin regimen for 12 and 24 weeks, respectively. Grade 3 hemoglobin values were rare. The decline in hemoglobin was largely managed with ribavirin dose reductions; use of hematologic growth factors and blood transfusion were rare. The

anemia reported in the clinical trials was primarily observed when the 3-DAA regimen was administered with ribavirin.

Transient asymptomatic post-baseline serum alanine aminotransferase (ALT) elevations of > 5 times upper limit of normal (ULN) occurred at a frequency of 1% across active treatment arms and were evaluated by an external hepatic panel. The serum (ALT) elevations were asymptomatic, usually occurred within the first four weeks of treatment and typically declined with ongoing treatment. A disproportionate number of the cases were in women on concurrent systemic estrogen-containing therapy (i.e. contraceptives or hormone replacement) and discontinuation of the hormonal therapy with continuation or brief interruption of the direct-acting antiviral regimen led to resolution in ALT elevation. Concomitant use of systemic estrogen-containing medications is a risk factor for these post-baseline elevations in serum alanine aminotransferase. No serum ALT elevations > 5 times ULN were observed in subjects receiving progestin only, or in subjects receiving topical vaginal estrogen preparations. Among the cases of serum ALT elevation, considered related to the direct-acting antiviral regimen, none resulted in hepatic dysfunction and they generally resolved or improved with ongoing treatment. All cases had resolved completely in the post-treatment follow-up.

ABT-450/ritonavir, ABT-267 (ombitasvir) (and its major, inactive human metabolites) and ABT-333 (dasabuvir) had no effects on embryo-fetal development in rodent and/or non-rodent species at maximal feasible exposures that provided area under the curve (AUC) multiples at least 4-fold higher than exposures at the recommended clinical doses. Clinical studies in women who are pregnant have not been conducted.

In summary, the three direct-acting antiviral (3-DAA) agents regimen, with or without ribavirin, was well tolerated with a low discontinuation rate. Adverse events were typically mild, and many of the adverse events and laboratory abnormalities observed were attributable to the presence of ribavirin.

Transient, asymptomatic serum alanine aminotransferase (ALT) elevations were observed at a low rate, were not associated with hepatic dysfunction, and generally resolved with ongoing treatment.

## **1.5 Study Risks versus Benefits**

ABT-450/ritonavir, ABT-267 (ombitasvir) and ABT-333 (dasabuvir) with or without ribavirin have been well tolerated in the Phase 3 studies. Adverse events that are known, and those not previously described, may occur with the direct-acting antivirals or ribavirin as detailed in the informed consent for this study. In addition, subjects may experience inconvenience or discomfort related to the study visits or study procedures.

Risks associated with ABT-450/ritonavir/ABT-267 (ombitasvir) and ABT-333 (dasabuvir) co-administered with or without ribavirin, including the risks of toxicity and virologic failure, appear limited and manageable based on the results from the Phase 3 studies. Given the potential high rate of cure in hepatitis C virus genotype 1-infected subjects, the risk-benefit comparison is favorable.

This study will evaluate outcomes with ABT-450/ritonavir/ABT-267 (ombitasvir) and ABT-333 (dasabuvir) with or without ribavirin for treatment-naïve and interferon/ribavirin treatment-experienced adults with chronic HCV genotype 1-infection without cirrhosis in a real world setting. A non-cirrhotic population will be evaluated as this is a group that is not considered of highest priority according to current national practice guidelines and therefore, largely unstudied in a large real world population.

Until recently, the treatment of genotype 1 chronic HCV infection involved complicated interferon-containing regimens associated with many side effects. Due to adverse events and patient dropout, outcomes in real world settings during and after treatment with these regimens have been inferior to those seen in controlled clinical trials. The cure rate (sustained virological response) and the effectiveness of treatment has been reported to be low in real world settings using interferon-based treatment regimens. In a Veterans Administration study by Kramer et al, only 39.9% of genotype 1 patients who completed treatment and only 23.6% of those who initiated treatment achieved sustained virological response. Importantly, treatment effectiveness (defined as the proportion of the viremic cohort who achieved sustained virological response) was very low at only 3.5%.

### **FDA Approval**

On December 19, 2014, the FDA Approved ABT-450/ritonavir, ABT-267 (ombitasvir) and ABT-333 (dasabuvir) as VIEKIRA PAK™ (ombitasvir, paritaprevir, and ritonavir tablets, 12.5 mg/ 75 mg/ 50 mg; dasabuvir tablets, 250 mg), co-packaged for oral use with or without ribavirin for the treatment of patients with genotype 1 chronic hepatitis C virus (HCV) infection including those with compensated cirrhosis.

### **1.6 Hypothesis**

Since the new treatment regimens do not cause the adverse events associated with the prior therapy, our hypothesis is that treatment with the VIEKIRA PAK (ombitasvir, paritaprevir/r, dasabuvir) with or without ribavirin will result in excellent outcomes in the real world setting and that the outcomes will be similar to those seen in the registration trials.

## **2 OBJECTIVES**

### **2.1 Primary Objective**

The primary objective of this open label study is to evaluate the rate of sustained virological response rate 12 weeks after completion of treatment (SVR12) with VIEKIRA PAK (ombitasvir, paritaprevir/r, dasabuvir), with or without ribavirin in a large real world setting.

### **2.2 Secondary Objective**

The secondary objectives of the study are as follows:

- To evaluate sustained virological response rate 4 weeks after completion of treatment (SVR4) with VIEKIRA PAK (ombitasvir, paritaprevir/r, dasabuvir), with or without ribavirin in a large real world setting
- To evaluate patient adherence with VIEKIRA PAK (ombitasvir, paritaprevir/r, dasabuvir), with or without ribavirin in a real world setting

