## 5 SELECTION OF SUBJECTS

### 5.1 Inclusion Criteria

To participate in this study the subject must **meet all** of the following inclusion criteria:

1. Male or female at least 18 years of age at time of screening.
2. Subject voluntarily signed the Informed Consent Form for the study.
3. Subject is able to adhere to study visit/ procedure schedule and protocol requirements
4. Subject, if female must not use estrogen-containing hormonal contraception including oral, injectable, implantable, patch and ring varieties during study drug treatment
5. Subject, if female must meet at least one of the following:
  - Subject of childbearing potential must agree to either
    - practice 2 effective contraceptive methods for study duration, starting Screening through 30 days after stopping study drug if not receiving ribavirin, 6 months/or as directed by ribavirin label if receiving ribavirin
    - practice total abstinence from sexual intercourse (minimum 1 complete menstrual cycle)
    - be sexually active with female partner only
  - Postmenopausal defined as age appropriate amenorrhea for  $\geq 2$  years prior to screening and post-menopausal state confirmed by follicle-stimulating hormone (FSH) level
  - Surgically sterile defined as bilateral tubal ligation or bilateral oophorectomy or hysterectomy
  - Has male sexual partner with vasectomy
6. Subject, if male, who is not surgically sterile and is sexually active with female partner of childbearing potential must agree to practice 2 effective contraceptive methods for study duration, starting at Screening through 30 days after stopping study drug if not receiving ribavirin, 7 months/or as directed by ribavirin label if receiving ribavirin
7. Subject must have at least one of the following indicators of chronic hepatitis C virus infection prior to study enrollment:
  - Positive anti-HCV antibody or HCV RNA  $> 10,000$  IU/mL at least 6 months before screening, and positive for HCV RNA at the time of screening
  - HCV RNA  $> 10,000$  IU/mL at screening and liver biopsy consistent with chronic HCV infection
  - Credible evidence of chronic hepatitis C as per the investigator and HCV RNA  $> 10,000$  IU/mL at the time of screening.
8. Subject has a screening laboratory result indicating HCV genotype 1-infection. Historical genotype within 6 months of screening may be used at the discretion of the investigator.

---

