### **6.3.2 Investigator Initiated Discontinuation**

The investigator may also discontinue a subject from the study at any time for the following reasons:

- Subject or subject's partner experiences AE or toxicity from the study drug that warrants discontinuation, or
- Subject is noncompliant (e.g. missed treatment doses, or missed visits) with the protocol, or
- If a subject has an ongoing AE or an unresolved laboratory result that is significantly outside of the reference range at the time of study drug discontinuation, the investigator will attempt to provide follow-up until a satisfactory clinical resolution of the laboratory result or AE is resolved.

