## **8.3 Efficacy Analysis**

The primary efficacy analysis on clinical outcomes will be performed on all subjects in the intent to treat population. All other efficacy analyses will be performed on the modified intent to treat population

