### **8.3.2 Secondary Efficacy Endpoint**

The secondary efficacy endpoints are:

- To assess SVR4. The simple percentage of subjects achieving SVR4 will be calculated and a two-sided 95% confidence interval of the percentage will be computed based on Wilson's score method.
- Patient adherence with the VIEKIRA PAK regimen will be evaluated by review of study drug returned for drug reconciliation and/or compilation of patient reported compliance information.

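### Section 6.3.2 lets investigators end study participation for missed doses or visits although adherence is a secondary objective, so adherence can be overstated and SVR12 in poor adherers can go unobserved

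*Combined protocol and SAP*

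**What the plan says.** All references are to the combined protocol and SAP.

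- **Objective.** Section 2.2 lists, as a secondary objective, "To evaluate patient adherence with VIEKIRA PAK (ombitasvir, paritaprevir/r, dasabuvir), with or without ribavirin in a real world setting".
- **Removal rule.** Section 6.3.2 reads "The investigator may also discontinue a subject from the study at any time for the following reasons", and one of the listed reasons is "Subject is noncompliant (e.g. missed treatment doses, or missed visits) with the protocol". The rule is discretionary, and it concerns the study as a whole. Section 6.3.3 shows that the protocol can separate the two: confirmed virologic failure on treatment ends treatment, and confirmed failure after treatment ends study participation.
- **Measure.** Under section 8.3.2 adherence is "evaluated by review of study drug returned for drug reconciliation and/or compilation of patient reported compliance information". No formula, denominator or rule for discontinued subjects follows.
- **Population.** Section 8.3 says "All other efficacy analyses will be performed on the modified intent to treat population". Section 8 defines that population as everyone dosed at least once, and it allows no imputation except for HCV RNA endpoints.
- **Collection.** Section 6.1.12 has drug reconciliation and adherence reviewed at each visit, and Appendix A schedules accountability from Baseline to Week 12/End of Treatment (EOT). The shared post-treatment Week 12/Early Termination (ET) column has no accountability entry, nor has the procedure list in section 6.2.4.2.
- **After stopping.** For subjects who leave during treatment, sections 6.2.3 and 6.2.4.2 encourage both the EOT procedures (which include accountability) and the ET visit within 14 days of last dose. Section 6.3.1, which covers discontinuation from any cause, names only the ET visit. It also has the last dose and the reason for stopping recorded.

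**The concern.** Poor adherence is both an outcome of the study and a permitted reason to stop observing a subject. Two things are at stake.

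The first is the adherence figure. With no formula and no rule for removed subjects, an analyst could report completers only, or pool doses over the time each subject was observed. Both give too little weight to the people removed for missing doses.

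The second is virologic outcome. A subject removed during treatment is directed to a last visit soon after the last dose, well before SVR12 can be assessed. Section 1.5 says that real-world results with the older interferon regimens fell short partly because of dropout. Poor adherers are therefore a group whose outcome a real-world study has particular reason to observe.

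**Working it through.** The plan states no expected adherence, no removal rate and no precision for adherence, so there is no figure to reproduce. The check has two parts.

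**1. Adherence under different denominators**

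From the documents: treatment is planned for 12 weeks (84 days) in both arms (section 4.4, Table 4).

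Assumed, not from the documents:
- retained subjects take r = 97% of doses;
- removed subjects take a = 50% or 70% while in the study;
- removal is at week t = 4 or 8, with dosing ending then;
- the share removed, f, is 1% to 10%.

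The reference is what would have been seen with no removal and unchanged adherence for 12 weeks:
- Reference: (1 - f)r + fa
- Completers only: r
- Subject-level mean to removal: (1 - f)r + fa
- Pooled doses to removal: [12(1 - f)r + tfa] / [12(1 - f) + tf]
- Planned 84 days: (1 - f)r + fa(t/12)

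With f = 5%, t = 4 and a = 50%:
- Reference: 0.95 × 97 + 0.05 × 50 = 92.15 + 2.50 = 94.65%
- Completers: 97.00%, which is 2.35 points too high
- Subject-level mean to removal: 94.65%, no difference
- Pooled: (12 × 0.95 × 97 + 4 × 0.05 × 50) / (12 × 0.95 + 4 × 0.05) = 1115.8 / 11.6 = 96.19%, which is 1.54 points too high
- Planned 84 days: 92.15 + 2.50 × 4/12 = 92.98%, which is 1.67 points too low

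Over the whole assumed range:

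| Calculation | Smallest difference | Largest difference |
|---|---|---|
| Completers only, f(r - a) | 0.01 × 27 = +0.3 | 0.10 × 47 = +4.7 |
| Pooled doses to removal | 96.82 - 96.73 = +0.1 (f = 1%, t = 8, a = 70%) | 95.32 - 92.30 = +3.0 (f = 10%, t = 4, a = 50%) |
| Subject-level mean to removal | 0 | 0 |
| Planned 84 days, -fa(1 - t/12) | 0.01 × 50 × 1/3 = -0.2 | 0.10 × 70 × 2/3 = -4.7 |

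Differences are in percentage points from the reference. The sign depends on a choice the plan has not made.

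**2. Timing of the last HCV RNA sample**

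The ET visit is to take place within 14 days of last dose (sections 6.2.3, 6.2.4.2 and 6.3.1). Section 8 sets the SVR12 window at post-treatment days 57 to 168. A sample on day 14 is 57 - 14 = 43 days before the window opens. A subject removed during treatment whose last sample is at ET therefore has no value from which SVR12 can be determined. HCV RNA endpoints are the one exception to the no-imputation rule, but section 8 does not say how they are imputed. In a genotype group of 100, the size assumed in section 8.3.1, one such subject moves the SVR12 percentage by up to 1/100 = 1 point, according to how that subject is classified.

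**The case against.** The strongest reply is that nobody leaves the analysis. Adherence falls under the mITT rule, so a removed subject stays in the population. Counts at earlier visits exist: someone removed at Week 4 has scheduled counts at Weeks 2 and 4. Patient report is a second source if packs are not returned. EOT procedures, with accountability, are encouraged after an on-treatment stop, and the reason for stopping is recorded. The removal clause is permissive, and the endpoint is descriptive.

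Most of this stands. A reader might infer that the worst adherers drop out of the measurement and that reported adherence will necessarily be too high. The documents support neither inference. The mITT rule and the visit-by-visit records contradict the first. The second fails because a subject-level mean to removal reproduces the reference, and an 84-day denominator falls below it.

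Two further inferences also go too far. One is that sites using the clause more often will look more adherent; no site comparison is planned. The other is that screening on ability to adhere (inclusion 3, "Subject is able to adhere to study visit/ procedure schedule and protocol requirements", and exclusion 15 on drug or alcohol abuse) is an error. Those criteria openly define the population to which the estimate applies.

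What the reply does not meet is that belonging to the population is not the same as having a value. A subject who misses visits, one of the named grounds for removal, yields no drug count at those visits. The final count is optional, adherence is not imputed, and nothing in 8.3.2 rules out a completer-based or pooled summary. Nor does the reply touch the SVR12 timing.

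**Conclusion.** The point holds in a limited form. Sections 2.2 and 6.3.2 pull against each other: the study may stop observing a subject because of the outcome it sets out to describe. Adherence can be overstated by about 0.1 to 4.7 points if it is computed on completers or on pooled doses to removal. It is not biased for a subject-level mean to removal, provided adherence would have stayed constant. These sizes rest wholly on the assumed adherence levels, removal times and removal share of 1% to 10%.

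SVR12 in subjects removed during treatment goes unobserved unless an HCV RNA result from days 57 to 168 is obtained in some other way. No direction or size of bias in SVR12 can be claimed, because the documents give neither the number of removals nor the imputation rule.

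**What to change.** 1. **Section 6.3.2.** Reconcile it with section 2.2. State that missed doses or visits are recorded as outcome data and are not by themselves a reason to end study follow-up or data collection, including the post-treatment Week 4 and Week 12 HCV RNA samples. Decisions on study drug stay as they are now.
2. **Section 6.2.4.2 and Appendix A.** Add study drug accountability to the ET visit for subjects who stop during treatment.
3. **Section 8.3.2.** Report adherence in all mITT subjects up to last dose, as a mean of subject-level values. Give adherence over the planned 84 days as a companion figure, and report the number stopped for noncompliance separately.

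The 84-day figure should not stand alone, because it counts doses not taken after an investigator's decision as the patient's non-adherence. It is still needed, because a figure that ends at the last dose hides patients who stop early of their own accord.

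The cost is protocol wording, one added ET procedure, some effort to follow subjects who attend poorly, and possibly a less favourable adherence figure.
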